4.2. Exclusion Criteria

Any potential subject who meets any of the following criteria will be excluded from participating in the study:

1. Treatment with any other investigational agent or participation in another clinical study with therapeutic intent within 30 days prior to C1D1. For Phase 1b, subjects who have received the following prior anti-tumor therapy:
 - Received nitrosoureas and mitomycin C within 6 weeks.
2. Criterion modified per Amendment 3

2.1 Phase 1b erdafitinib + cetrelimab cohort:

- Chemotherapy within 3 weeks of C1D1.

Phase 1b erdafitinib + cetrelimab + platinum chemotherapy cohort and Phase 2:

- Prior neoadjuvant/adjuvant chemotherapy is allowed if the last dose was given >12 months prior to recurrent disease progression and did not result in drug-related toxicity leading to treatment discontinuation.

3. Criterion modified per Amendment 2

3.1 Criterion modified per Amendment 3

3.2 Prior anti-PD-1, anti-PD-L1, or anti-PD-L2 therapy. Prior neoadjuvant/adjuvant checkpoint inhibitor therapy is allowed if the last dose was given >12 months prior to recurrent disease progression and did not result in drug-related toxicity leading to treatment discontinuation. PD-1 for non-muscle invasive bladder cancer is also allowed.

4. Criterion modified per Amendment 2

4.1 Active malignancies requiring concurrent therapy other than urothelial cancer.

5. Symptomatic central nervous system metastases.

6. Prior FGFR inhibitor treatment.

7. Radiation therapy ≤30 days prior to planned C1D1.

8. Criterion modified per Amendment 2

8.1 Criterion modified per Amendment 3

8.2 History of uncontrolled cardiovascular disease including:

- Unstable angina, myocardial infarction, ventricular fibrillation, Torsades de Pointes, cardiac arrest, or known congestive heart failure Class III-V ([Attachment 6](#)) within the preceding 3 months; cerebrovascular accident or transient ischemic attack within the preceding 3 months.

9. Known to be seropositive for human immunodeficiency virus or acquired immune deficiency syndrome.

10. Any of the following:

- Evidence of serious active viral, bacterial, or uncontrolled systemic fungal infection.

- Active autoimmune disease or a documented history of autoimmune disease that requires systemic steroids or immunosuppressive agents.

Note: Subjects with vitiligo or resolved childhood asthma/atopy would be an exception to this rule. Subjects that require intermittent use of bronchodilators or local steroid injections would not be excluded from the study. Subjects with hypothyroidism stable on hormone replacement will not be excluded from the study. Subjects with a history of transient autoimmune manifestations of an acute infectious disease that resolved upon treatment of the infectious agent (eg, acute Lyme arthritis) will not be excluded from the study.

- Grade 3 or higher toxicity effects from previous treatment with immunotherapy.
- Psychiatric conditions (eg, alcohol or drug abuse), dementia, or altered mental status.
- Any other issue that would impair the ability of the subject to receive or tolerate the planned treatment at the investigational site, to understand informed consent or any condition for which, in the opinion of the investigator, participation would not be in the best interest of the subject (eg, compromise the well-being) or that could prevent, limit, or confound the protocol-specified assessments.

11. Pulmonary compromise requiring supplemental oxygen use to maintain adequate oxygenation.
12. Active or chronic hepatitis B or hepatitis C disease as determined by hepatitis B surface antigen (HBsAg), hepatitis B core antibody, or hepatitis C antibody (anti-HCV) positivity at Screening. If positive, further testing of quantitative levels to rule out active infection is required (see [Attachment 2](#)).

13. Criterion modified per Amendment 3

13.1 Phase 1b erdafitinib + cetrelimab and **Phase 1b erdafitinib + cetrelimab + platinum chemotherapy cohort:** Not recovered from reversible toxicity of prior anticancer therapy (except toxicities which are considered by the investigator as not clinically significant, such as alopecia, skin discoloration, or Grade 1 hearing loss or neuropathy).

Phase 2: Not recovered from reversible toxicity of prior anticancer therapy (except toxicities which are considered by the investigator as not clinically significant such as alopecia, or skin discoloration).

14. Impaired wound healing capacity defined as skin/decubitus ulcers, chronic leg ulcers, known gastric ulcers, or unhealed incisions.
15. Criterion modified per Amendment 2

15.1 Allergies, hypersensitivity, or intolerance to protein-based therapies or with a history of any significant drug allergy (such as anaphylaxis, hepatotoxicity, or

immune-mediated thrombocytopenia or anemia), or to excipients of erdafitinib or cetrelimab (see the Investigator's Brochures for a list of excipients).

16. Criterion modified per Amendment 2

16.1 Current central serous retinopathy (CSR) or retinal pigment epithelial detachment (RPED) of any Grade.

17. Criterion deleted per Amendment 2

18. Criterion modified per Amendment 2

18.1 Use of immunosuppressant agents, including, but not limited to: systemic corticosteroids at doses exceeding 10 mg/day of prednisone or its equivalent, methotrexate, cyclosporine, azathioprine, and tumor necrosis factor α (TNF- α) blockers, within 2 weeks before the planned first dose of study drug.

19. Vaccinated with a live attenuated vaccine within 28 days prior to the first dose of study drug and for 3 months after receiving the last dose of study drug. Annual inactivated influenza vaccine is permitted.

20. Criterion modified per Amendment 3

20.1 Phase 1b erdafitinib + cetrelimab cohort and Phase 2: Pregnant or breast-feeding, or planning to become pregnant while enrolled in this study or within 5 months after receiving the last dose of study drug.

Phase 1b erdafitinib + cetrelimab + platinum chemotherapy cohort: Pregnant or breast-feeding, or planning to become pregnant while enrolled in this study or within 6 months after receiving the last dose of study drug.

21. Criterion modified per Amendment 3

21.1 Phase 1b erdafitinib + cetrelimab cohort and Phase 2: Plans to father a child while enrolled in this study or within 5 months after receiving the last dose of study drug.

Phase 1b erdafitinib + cetrelimab + platinum chemotherapy cohort: Plans to father a child while enrolled in this study or within 6 months after receiving the last dose of study drug.

22. Criterion modified per Amendment 2

22.1 Major surgery within 4 weeks of enrollment, or inadequate recovery from the toxicity and/or complications from the intervention prior to starting therapy.

23. Criterion modified per Amendment 3

23.1 Phase 1b erdafitinib + cetrelimab cohort and Phase 2: not applicable.

Phase 1b erdafitinib + cetrelimab + platinum chemotherapy cohort: known sensitivity to any component of cisplatin or carboplatin.

NOTE: Investigators should ensure that all study enrollment criteria have been met at Screening. If a subject's clinical status changes (including any available laboratory results or receipt of additional medical records) after Screening but before the first dose of study drug is given such that he or she no longer meets all eligibility criteria, then the subject should be excluded from participation in the study. Section 9.1.2 describes options for retesting. Section 17.4 describes the required documentation to support meeting the enrollment criteria.

5. TREATMENT ALLOCATION AND BLINDING

This is an open-label study. No blinding procedures will be applied.

Subjects will be enrolled sequentially to a dose level after a discussion between the investigator and the sponsor.

6. DOSAGE AND ADMINISTRATION

Erdafitinib, along with cetrelimab and platinum (cisplatin or carboplatin) chemotherapy infusions will be administered on the same day. Erdafitinib will be administered first, followed by cetrelimab and then platinum chemotherapy.

6.1. Dose Combination for Erdafitinib + Cetrelimab + Platinum Chemotherapy Cohort

Erdafitinib (8 mg oral without up-titration), cetrelimab (360 mg Q3W IV) and platinum chemotherapy will be administered at a starting dose of cisplatin 50 mg/m² Q3W IV in DL2C or carboplatin AUC 4 mg/mL/min Q3W IV in DL2D.

The dose levels for cisplatin and carboplatin are shown in [Appendix 2 Table 4](#).

Appendix 2 Table 4: Erdafitinib, Cetrelimab, and Platinum Chemotherapy Administration: Dose Levels

Phase	Dosing Level ^{a, e}	Cisplatin or Carboplatin (IV infusion) ^{c, d}	Erdafitinib (oral administration) ^c	Cetrelimab (IV infusion) ^{b, c}
1b	DL2C	Cisplatin 50 mg/m ² Q3W		
1b	DL2C1	Cisplatin 60 mg/m ² Q3W		
1b	DL2D	Carboplatin AUC 4 mg/mL/min Q3W (Not to Exceed 600 mg)	8 mg (no up-titration) once daily	360 mg Q3W
1b	DL2D1	Carboplatin AUC 5 mg/mL/min Q3W (Not to Exceed 750 mg)		

^a Additional dosing schedules may be explored if recommended by the SET and agreed upon by the sponsor.

^b The cetrelimab dosing schedule can be adjusted if recommended by the SET and agreed upon by the sponsor.

^c On days that all study drugs will be administered, the sequence of administration will be erdafitinib first, followed by cetrelimab and then platinum chemotherapy

^d Erdafitinib + cetrelimab can continue every 3 weeks after a maximum of 4 cycles of platinum chemotherapy.

^e See Section 3.1.1 of Appendix 2 for dose escalation.

6.2. Administration of Erdafitinib

Refer to Section 6.2 of the main body of the protocol.

6.3. Administration of Cetrelimab

Refer to Section 6.3 of the main body of the protocol.

6.4. Administration of Platinum Chemotherapy (Cisplatin or Carboplatin)

Standard chemotherapeutic agents will be prepared and administered as per the approved product label at the doses indicated below.

6.4.1. Cisplatin

The starting dose level for of cisplatin (DL2C) is 50 mg/m² IV Q3W. The dose level escalation rules for cisplatin are described in Section 3.1.1 of this appendix. Dosing with cisplatin should be immediately preceded and followed by hydration procedures. Supportive premedication and administration procedures for cisplatin are to align with the cisplatin label and local practice. A maximum of 4 cycles of cisplatin are to be administered to the subject. Erdafitinib and cetrelimab will continue after the subject receives 4 cycles of cisplatin.

6.4.2. Carboplatin

The starting dose level for carboplatin (DL2D) is AUC 4 mg/mL/min Q3W. The dose level escalation rules for carboplatin are described in Section 3.1.1 of this appendix. Supportive premedication and administration procedures for carboplatin are to align with the carboplatin label and local practice. A maximum of 4 cycles of carboplatin are to be administered to the subject. Erdafitinib and cetrelimab will continue after the subject receives 4 cycles of carboplatin.

Carboplatin dosing is calculated via the Calvert formula. Carboplatin dosing is not to exceed 600 mg for AUC4 dose level, and 750 mg for AUC5 dose level.

Calvert Formula:

$$\text{Total Dose (mg)} = (\text{target AUC}) \times (\text{CrCl} + 25)$$

The estimated GFR used in the Calvert formula should not exceed 125 mL/min.

The maximum carboplatin dose (mg) = target AUC 4 (mg/min/mL) x (125 + 25) = 4 x 150 mL/min is 600 mg.

The calculation of the creatinine clearance can be found in [Attachment 8](#).

6.4.3. Antiemetic Therapy and Supportive Care Guidelines for Platinum Chemotherapy

Antiemetic therapy administered on days of platinum chemotherapy should follow Multinational Association for Supportive Care in Cancer (MASCC) guidelines (and should, for the first 4 cycles, include a 5-HT3 receptor antagonist, dexamethasone (or equivalent) and aprepitant (or equivalent) as per the MASCC guidelines.

Routine primary prophylaxis to treat immunosuppression is not permitted for subjects who are under evaluation for DLTs. For the use of CSFs after the DLT period ends, utilize ([NCCN/EORTC 2018](#)) guidelines. However, subjects should receive appropriate supportive care measures as deemed necessary by the treating investigator. For each disorder, attempts should be made to rule out other causes such as metastatic disease or bacterial or viral infection, which might require additional supportive care.

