8.1. Permitted Medications

Throughout the study, investigators may prescribe concomitant medications or treatments (including nutritional support, correction of metabolic disorders, optimal symptom control, and pain management) deemed necessary to provide adequate supportive care. Concurrent use of hormones for non-cancer related conditions (eg, insulin for diabetes and hormone replacement therapy) is acceptable. Concomitant medications (eg, acetaminophen/paracetamol or diphenhydramine) deemed necessary by the investigator to provide adequate prophylaxis and management of IRRs are allowed. Refer to Section [6.3.4](#) for guidance on medications to manage immune-related toxicities.

In addition, the following medications may be administered during the study:

- Standard supportive care therapies (antiemetics, antidiarrheals, anticholinergics, antispasmodics, antipyretics, antihistamines, analgesics, antibiotics and other antimicrobials, histamine receptor [H2] antagonists or proton pump inhibitors, and other medications intended to treat symptoms or signs of disease) as clinically indicated, according to institutional standards and as deemed necessary by the investigator.

- Permitted antiemetics include: aprepitant, ondansetron, and dexamethasone
- Documented infectious complication should be treated with oral or IV antibiotics or other anti-infective agents as considered appropriate by the treating investigator for a given infectious condition, according to standard institutional practice.
- In general, growth factor support is permitted for the management of treatment-emergent hematological toxicity as recommended according to National Comprehensive Cancer Network/European Organization for Research and Treatment of Cancer ([NCCN/EORTC 2018](#)) guidelines. Primary prophylaxis is not permitted for subjects who are under evaluation for DLTs.
- Palliative radiotherapy: Localized radiotherapy for symptomatic control is permitted but should not include definitive radiation to target lesions.
- Chronic supportive therapies: Ongoing bisphosphonates and denosumab or other supportive therapies are permitted.

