8.3. Precautions for Concomitant Medications, Food, and Surgical Intervention

The bioavailability and in consequence the safety as well as efficacy profile of the study drug may be altered when co-administered with medications or food listed in [Table 26](#). Therefore, these medications should be avoided, or should be administered with caution concomitantly with study therapy. Guidance for surgical intervention is also provided in this table.

Based on in vitro data, erdafitinib is metabolized by cytochrome CYP2C9 and CYP3A4. A clinical drug-drug interaction study showed that on average, erdafitinib exposure (C_{max} and AUC) was increased 5% to 34% when co-administered with itraconazole (a strong inhibitor of CYP3A4) and 21% to 49% when co-administered with fluconazole (a moderate inhibitor of CYP2C9). For this reason, strong CYP3A4 and moderate CYP2C9 inhibitors should be used with caution (see [Attachment 4](#)). Consider alternative therapies that are not strong inhibitors of CYP3A4 or moderate inhibitors of CYP2C9 during treatment with erdafitinib. If co-administration of these drugs is unavoidable, monitor the subject closely for adverse reactions and consider dose modifications accordingly. If the strong inhibitor of CYP3A or moderate inhibitor of CYP2C9 is discontinued, the erdafitinib dose may be increased up to the maximum of 9 mg daily in the absence of drug-related toxicity.

The impact of moderate CYP2C9 inducers and strong CYP3A inducers (such as rifampin) on erdafitinib was not clinically studied. Co-administration of erdafitinib with these agents may significantly decrease erdafitinib exposure. Therefore, the concomitant use of these agents with erdafitinib should be avoided (see [Attachment 4](#)). Co-administration of erdafitinib with moderate CYP3A inducers may decrease erdafitinib exposure. Caution should be exercised for concomitant administration of erdafitinib and moderate inducers of CYP3A4 (see [Attachment 4](#)).

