Erdafitinib was shown to inhibit, in in vitro experiments, human P-glycoprotein (P-gp) at the concentrations achieved at therapeutic doses in humans. If co-administration of erdafitinib with P-gp substrates is unavoidable, separate erdafitinib administration by at least 6 hours before or after administration of P-gp substrates with narrow therapeutic index (<https://www.fda.gov/downloads/drugs/guidances/ucm292362.pdf>); in addition, drugs with a narrow therapeutic index should only be used when the benefit outweighs the potential risk.

Table 26: Concomitant Medications and Surgical Interventions to be Avoided or to be Used With Caution

Moderate CYP2C9 inducers and strong CYP3A inducers

 Co-administration of erdafitinib with these agents may significantly decrease erdafitinib exposure. Therefore, the concomitant use of these agents with erdafitinib should be avoided.
Moderate or strong CYP2C9 and CYP3A inhibitors, moderate CYP3A inducers

 Moderate or strong in vivo inhibitors of CYP3A and CYP2C9 enzymes should be used with caution¹ Moderate in vivo inducers of CYP3A enzyme¹ should be used with caution
QT-Prolonging Agents

 Medications known to cause Torsades de Pointes²
P-gp Substrates

 P-gp substrates with narrow therapeutic index (eg, digoxin)
Medications Known to Increase Serum Levels of Phosphate

 Phosphate supplements (oral or IV), vitamin D supplements, antacids, and phosphate-containing enemas & laxatives (oral/rectal)

Surgical Intervention

• Held at least 3 to 7 days pre- and post-surgery depending upon the type of surgery and the risk of bleeding

Abbreviations: P-gp = P-glycoprotein

1. For a listing of CYP3A and CYP2C9 inhibitors and inducers see [Attachment 4](#).
2. For a listing of medications that cause QT prolongation see http://www.acert.org/medical-pros/drug-lists/list-01.cfm?sort=Generic_name.

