Attachment 3: Eastern Cooperative Oncology Group Performance Status Grade

Grade	Eastern Cooperative Oncology Group Performance Status
0	Fully active, able to carry on all pre-disease performance without restriction
1	Restricted in physically strenuous activity but ambulatory and able to carry out work of a light or sedentary nature, eg, light housework, office work
2	Ambulatory and capable of all self-care but unable to carry out any work activities. Up and about more than 50% of waking hours
3	Capable of only limited self-care, confined to bed or chair more than 50% of waking hours
4	Completely disabled. Cannot carry on any self-care. Totally confined to bed or chair
5	Dead

[Oken 1982](#)

Attachment 4: Drugs Classified as Strong CYP3A4 Inhibitors, Moderate to Strong CYP3A4 Inducers, Moderate CYP2C9 Inhibitors, and Moderate CYP2C9 Inducers

Strong CYP3A4 Inhibitors

Boceprevir	Conivaptan
Clarithromycin	Indinavir
Grapefruit juice	Itraconazole
Lopinavir	Ketoconazole
Mibepradil	Ritonavir
Nefazodone	Nelfinavir
Posaconazole	Conivaptan
Saquinavir	Boceprevir
Telaprevir	Clarithromycin
Telithromycin	Erythromycin
Voriconazole	Troleandomycin
Fluconazole	

Strong Inhibitors: ≥ 5 -fold increase in AUC or $> 80\%$ decrease in CL.

Moderate to Strong CYP3A4 Inducers

Moderate CYP3A4 Inducers	
Bosentan	Efavirenz
Etravirine	Modafinil
Nafcillin	Lersivirine
Talvirinaline	Tipranavir
Lopinavir	
Strong CYP3A Inducers	
Avasimibe	Carbamazepine
Barbiturates eg, phenobarbital	Phenytoin
Rifabutin	Rifampin
St. John's wort	Mitotane
Enzalutamide	Apalutamide

Strong Inducers: $\geq 80\%$ decrease in area under the curve (AUC). Moderate Inducers: 50% to 80% decrease in AUC.

Moderate CYP2C9 Inhibitors

Fluconazole	amiodarone
Miconazole	piperine
Oxandrolone	ataciguat
tienilic acid	azapropazone
Bucolome	sulfaphenazole
Benzbromarone	

Moderate CYP2C9 Inducers

Carbamazepine	rifampin
Enzalutamide	aprepitant

Reference: University of Washington's Drug Interaction Database

<http://www.fda.gov/Drugs/DevelopmentApprovalProcess/DevelopmentResources/DrugInteractionsLabeling/ucm093664.htm#4>

Both these references may not be exhaustive and up-to-date at any given time. Please consult the product information of ongoing and new concomitant medications for the most accurate information on potential moderate to strong inhibitors or inducers of CYP3A4 and CYP2C9.

[figure not shown]

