Abbreviations: AE = adverse event; aPTT = activated partial thromboplastin time; b-hCG= beta-human chorionic gonadotropin; C = cycle; CR= complete response; CT = computed tomography; ctDNA=circulating tumor DNA; D = day; ECG = electrocardiogram; ECOG = Eastern Cooperative Oncology Group; EOI=end of infusion; FGFR= fibroblast growth factor receptor; FT4= free thyroxine; ICF = informed consent form; INR = international normalized ration; MRI = magnetic resonance imaging; MUGA= multi-gated acquisition scan; OCT = optical coherence tomography; PBMC=peripheral blood mononuclear cell; PD-L1 = programmed cell death ligand 1; PE = physical examination; PK = pharmacokinetics; PO ₄ = phosphate; PR= partial response; PS = performance status; PT = prothrombin time; PTH=parathyroid hormone; RECIST = Response Evaluation Criteria in Solid Tumors; RP2D=recommended Phase 2 dose; T3= triiodothyronine; TCR=T cell antigen receptor; TSH= thyroid stimulating hormone																
^a The End-of-Treatment Visit will occur within 30 days after the subject discontinues treatment for any reason. This assessment should be done prior to the subject starting a new therapy. Follow-up visits will occur every 12 weeks (±7 days).																
^b For subjects signing a Full-Study ICF for the purpose of undergoing a new tissue biopsy for molecular screening, the 35-day window starts with the first planned study-related procedure other than the tissue biopsy; however, AEs will need to be collected from the time of Full-Study ICF sign off.																
^c Physical examination, vital signs, and pregnancy testing at first follow-up visit (12 weeks after last dose).																
^d On Day 1 of Cycles 1 through 4, erdafitinib oral dose will be given before the start of cetrelimab infusion, followed by platinum (cisplatin or carboplatin) chemotherapy. Pre-dose PK sample for erdafitinib to be taken within 30 mins before Pre-infusion PK (cetrelimab and platinum [cisplatin or carboplatin] chemotherapy), and immunogenicity samples for cetrelimab collected within 30 mins before cetrelimab infusion begins.																
^e C1D1 must occur no more than 3 days after the Enrollment transaction in IWRS.																
^f Cisplatin and carboplatin dosing will occur on Day 1 of each cycle for a maximum of 4 cycles.																
^g Guidance for study conduct for ongoing subjects in the event of a national disaster is provided in Attachment 10 .																

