Appendix 2: Phase 1b Erdafitinib + Cetrelimab + Platinum Chemotherapy Cohort

CONFIDENTIAL – FOIA Exemptions Apply in U.S.

198

Appendix 2 Table 2: Pharmacokinetic, Immunogenicity, and Biomarker Samples for the Phase 1b Erdafitinib+ Cetrelimab + Platinum Chemotherapy Cohort (Up to and Including Amendment 4)

Assessments/ Procedure	Notes	Molecular Eligibility Screening Period	Full-Study Screening Period	Treatment Cycle 1			Treatment Cycle 2			Treatment Cycle 3	Treatment Cycle 4			All Other Cycles	End-of- Treatment ^a	Follow- up Period ^a
		≥28 days prior to C1D1	Within 28 days prior to C1D1	Day 1	Day 8 (±2)	Day 15 (±2)	Day 1 (±2)	Day 8 (±2)	Day 15 (±2)	Day 1 (±2)	Day 1 (±2)	Day 8 (±2)	Day 15 (±2)	Day 1 (±2)	Within 30 Days (+7) of last dose	Every 12 weeks
Note: These samples should be drawn on the day study drug is administered. ^b																
Erdafitinib PK ^c	Pre-dose erdafitinib ^e unless otherwise specified. See Section 9.3.			X	X	X	Pre-dose and 4h post- dose			X				C5D1, pre-dose and 4h post erdafitinib dose		
Erdafitinib Protein Binding Blood Sample	4 h Post-dose See Section 9.3.						X									
Cetrelimab PK ^c	Pre-infusion ^d and EOI ^f unless otherwise specified; See footnote h for detailed sampling timepoints for cycles after Cycle 3; not all samples are taken on Day 1. See Section 9.3.			X	X Any time dur- ing visit	X Any time dur-ing visit	X			X	X ^h	X ^h	X ^h	X ^h	X Any time during visit	At first follow-up visit, if possible
Cetrelimab Immunogenicity	Pre-infusion ^d See Section 9.3.			X		X	X			X	X			Pre- infusion for C5. Then every other cycle after C5	X Any time during visit	At first follow-up visit, if possible
Cisplatin PK ⁱ (Cohort DL2C+ DL2C1)				X			X			X	X					
Carboplatin PK ^j (Cohort DL2D + DL2D1)				X			X			X	X					
CCI [REDACTED]	Pre-dose erdafitinib ^d			X	X	X	X									

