3.3.1. Definition of Dose-Limiting Toxicity for Phase 1b (Dose Escalation)

Toxicities will be graded for severity according to the NCI-CTCAE, version 5.0. Only toxicities that occur during the DLT evaluation period will be used to define DLTs and for dose escalation decisions, but toxicities that occur during the entire treatment period will be recorded and considered in decisions regarding the RP2D.

The DLT evaluation period for the Phase 1b erdafitinib + cetrelimab + platinum (cisplatin or carboplatin) chemotherapy cohort is defined as 2 full cycles (6 weeks) of erdafitinib, cetrelimab, and platinum chemotherapy from the start of the first erdafitinib dose.

If the subject receives more than 75% of any of the study drugs in the DLT evaluation period, the subject will be evaluable for DLT. If the subject received less than 75% of each assigned dose due to reasons other than toxicities (eg, disease progression, missed appointments, non-compliance, subject withdrawal), the subject may be replaced with a new subject. All available safety data from subjects will be taken into consideration by the SET. Dose-limiting toxicities are defined as any of the events listed in [Appendix 2 Table 3](#).

Appendix 2 Table 3: Dose-Limiting Toxicity Criteria for Phase 1b: Erdafitinib + Cetrelimab + Platinum Chemotherapy cohort

Criteria for Non-hematological Toxicity	
	Exceptions
• Any Grade 3	Asthenia, anorexia, fever, or constipation
	Fatigue that improves to Grade ≤ 2 in ≤ 7 days
	Nausea lasting for ≤ 7 days responding to BSC ^a
	Vomiting and diarrhea that resolves in ≤ 3 days with BSC ^a
	Laboratory abnormalities that do not require hospitalization and are not felt to be clinically significant by the investigator
	Tumor flare (defined as local pain, irritation, or rash localized at sites of known or suspected tumor) that improves to Grade ≤ 2 in ≤ 7 days
	Elevation in AST or ALT for <7 days
• Any Grade 4	None
• Any Grade 5	None
• Elevation in AST or ALT >3 x ULN meeting criteria for Hy's law ^b	
Criteria for Hematological Toxicity	
Neutrophil count decreased: Grade 4 for >7 days	
Febrile neutropenia: Grade ≥ 3 or 4	
Platelet count decreased: Grade 3 with clinically significant bleeding or Grade 4	
Any Grade 5 toxicity	

Abbreviations: ALT=alanine aminotransferase; AST=aspartate aminotransferase; BSC=best supportive care; ULN=upper limit of normal.

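### Aprepitant is named for platinum days in Appendix 2, yet it belongs to a drug class the protocol says to avoid with erdafitinib

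*Protocol*

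**What the plan says.** Five places in the protocol bear on this.

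- **Appendix 2, Section 6.4.3** states that antiemetic therapy on platinum days should, for the first 4 cycles, "include a 5-HT3 receptor antagonist, dexamethasone (or equivalent) and aprepitant (or equivalent) as per the MASCC guidelines".
- **Section 8.1** lists the drug without restriction: "Permitted antiemetics include: aprepitant, ondansetron, and dexamethasone".
- **Attachment 4** has a list headed "Moderate CYP2C9 Inducers" with four entries: carbamazepine, rifampin, enzalutamide and aprepitant.
- **Section 8.3** says "The impact of moderate CYP2C9 inducers and strong CYP3A inducers (such as rifampin) on erdafitinib was not clinically studied", adds that co-administration may significantly lower erdafitinib exposure, and concludes: "Therefore, the concomitant use of these agents with erdafitinib should be avoided". It refers the reader to Attachment 4.
- **Table 26** repeats that rule in a row for moderate CYP2C9 inducers and strong CYP3A inducers. A separate row covers agents that only call for caution.

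Appendix 2 Section 6 has erdafitinib, cetrelimab and platinum given on the same day, with erdafitinib first.

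**The concern.** Followed as written, the antiemetic section leads a site to the named drug and the interaction section leads it away from the same drug. Neither section acknowledges the other.

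The overlap falls where this cohort's primary endpoint is measured. The DLT period is "defined as 2 full cycles (6 weeks) of erdafitinib, cetrelimab, and platinum chemotherapy from the start of the first erdafitinib dose", so both of its platinum days are covered by the antiemetic instruction. Appendix 2 Table 3 also makes some Grade 3 nausea and vomiting exempt from DLT status depending on supportive care. The table's footnote defines that care by institutional standards or by Section 8.1, which is where aprepitant is permitted.

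If the protocol's own classification is right, erdafitinib exposure around platinum days could differ between subjects according to the antiemetic their site chose. Erdafitinib PK in the combination is a secondary objective of the cohort, and Appendix 2 Section 3.3.2 has the RP2D decision review all available PK data.

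**Working it through.** The check is a comparison of texts, followed by simple counts of how far the conflict could reach.

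**Is the conflict complete?**

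1. Drug named: aprepitant or an equivalent (Appendix 2 Section 6.4.3); aprepitant permitted by name (Section 8.1).
2. Class: Attachment 4 places aprepitant among the moderate CYP2C9 inducers. Section 8.3 and Table 26 do not name aprepitant; they set the rule for the class, and Section 8.3 points to Attachment 4 for its members.
3. Rule for the class: avoid with erdafitinib. Table 26 keeps this class apart from the caution-only rows.
4. Concomitant use: erdafitinib is taken once daily and on the same day as platinum.
5. Exception: none in Section 6.4.3, Section 8.1, Section 8.3, Table 26 or Attachment 4.

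The chain from the named drug to the avoid rule is therefore unbroken.

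**How many subjects?** Appendix 2 Section 3.1.1 plans 3 at the starting level, 6 at the escalated level and about 10 more at the maximum tolerated dose (MTD), for each platinum agent.

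- Per agent: 3 + 6 + 10 = 19.
- Both agents: 19 × 2 = 38, which the protocol rounds to approximately 40.
- Initial and escalated levels only: (3 + 6) × 2 = 18.

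These are upper limits, because the number who would actually receive aprepitant is not stated.

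**How many days?** Appendix 2 Table 1, footnote f: "Cisplatin and carboplatin dosing will occur on Day 1 of each cycle for a maximum of 4 cycles". Cycles last 21 days.

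- DLT window: 2 platinum days in 2 × 21 = 42 days, or 4.8%.
- Chemotherapy phase: 4 platinum days in 4 × 21 = 84 days, or 4.8%.

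These count the days that Section 6.4.3 covers. They do not measure how long any effect on exposure would last.

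**What would the PK schedule show?** The erdafitinib row of Appendix 2 Table 2 gives 8 scheduled samples:

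| Sample | Position relative to platinum days |
|---|---|
| C1D1 pre-dose | Before any platinum |
| C1D8 | 7 days after |
| C1D15 | 14 days after |
| C2D1 pre-dose | About 21 days after the previous one |
| C2D1 at 4 h | Post-dose on a platinum day |
| C3D1 pre-dose | About 21 days after the previous one |
| C5D1 pre-dose | After the 4-cycle maximum |
| C5D1 at 4 h | After the 4-cycle maximum |

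The last two rows come from the entry "C5D1, pre-dose and 4h post erdafitinib dose". One sample of 8 is post-dose on a platinum day. If an effect were short-lived, the schedule would say little about it. If it lasted a week or more, C1D8 and C1D15 could also carry information. The protocol gives no time course, so neither case can be preferred.

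**The case against.** The strongest reply is that the two sides are softer than they first look. Section 6.4.3 is a recommendation and allows an equivalent, so aprepitant is not compulsory. Section 8.3 is a precaution: its opening speaks of avoidance or caution, and CYP inducers do not appear in the prohibited list (Table 25). A site could also take the express permission in Section 8.1 as overriding a general class precaution. Attachment 4 itself warns that its sources may be incomplete or out of date.

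These points reduce the force of the conflict without removing it. The text specific to this class says avoid, and the protocol does not say which section governs. If Attachment 4 is imprecise, it is one of the texts to correct. The option of an equivalent helps only in part: the protocol names none, and because the lists may be incomplete, absence from Attachment 4 does not prove that a drug lies outside the class.

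Two further points stand. The link to DLT, RP2D or PK results is speculative on the documents alone, and the RP2D rests on PK, pharmacodynamic, safety and efficacy data together. The Amendment 5 schedule in Appendix 4 contains no platinum, so a correction changes nothing for subjects already on it. The protocol does not state whether platinum-cohort enrolment was still open.

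**Conclusion.** The point holds as an internal contradiction about one named drug and should be corrected. Confidence is high on the texts, which conflict when Section 6.4.3, Section 8.1, Section 8.3, Table 26 and Attachment 4 are read together.

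The reach is bounded by about 38 planned subjects, and within that by those whose site uses aprepitant. No bias or exposure change is claimed: Section 8.3 says the interaction was not studied clinically, and nothing in the protocol lets its size or duration be derived. The reading that the PK samples would be uninformative assumes a short-lived effect. Nothing here implies which of the conflicting instructions is clinically right.

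**What to change.** Reconcile Appendix 2 Section 6.4.3 and Section 8.1 with Section 8.3, Table 26 and Attachment 4, so that sites have a single instruction for aprepitant in subjects taking erdafitinib. Which text changes is the sponsor's clinical decision.

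As an optional addition for subjects already treated, flag aprepitant use by cycle in a descriptive listing beside the erdafitinib concentrations reviewed for the RP2D. Neither a comparison of Cycles 1 to 3 with Cycle 5 nor one of users with non-users should be read as isolating an aprepitant effect. The first is confounded with platinum, and the second may have no comparison group.

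The cost is a text correction in the affected sections and, if wanted, one flag in a listing. Section 8 already requires concomitant therapy to be recorded in the eCRF, so no new data collection is needed.
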